6.1.3.2. Maintenance Dosing Period Secondary Population

The number and percentage of patients achieving or maintaining a categorical efficacy and health outcome responses (that is, sPGA (0,1), sPGA (0), PASI 75, PASI 90, PASI 100, etc.) will be summarized by treatment group for all scheduled visits (NRI), including Week 60 (NRI).

Continuous efficacy and health outcomes measures will be summarized by treatment group at all scheduled visits during Period 3, including Week 60 (LOCF) using descriptive statistics (n, mean, SD, median, minimum and maximum).

The categorical safety measures will be summarized with incidence rates. The mean change of the continuous safety measures will be summarized at all scheduled visits.

6.1.3.3. Maintenance Dosing Period Relapse Population

For patients who were retreated with ixekizumab following loss of response (relapse), the proportion of patients maintaining or achieving categorical efficacy and health outcome responses (that is, sPGA (0,1), sPGA (0), PASI 75, PASI 90, PASI 100) within 12 weeks after ixekizumab retreatment will be summarized by treatment group. For the safety analyses on the

Maintenance Dosing Period Relapse population with ixekizumab retreatment, baseline is defined as the last non-missing assessment on or prior to the first dose of re-treatment. The treatment period for the Maintenance Dosing Period Relapse population with ixekizumab retreatment starts at the time of the relapse visit (first dose of re-treatment) and ends on the date of Week 60 (Visit 19) or the ETV (if it occurs between the relapse visit and Week 60).

The categorical safety measures will be summarized with incidence rates.

6.1.4. General Considerations for Analyses during Period 4 (Post-Treatment Follow-up Period)

For Period 4 safety analyses, baseline is defined as the last non-missing assessment on or prior to entering Period 4, i.e. on or prior to Week 60 (Visit 19) or ETV.

Selected safety data will be summarized using descriptive statistics.

6.2. Handling of Dropouts or Missing Data

The methods for imputation of missing data to be used in this study are in accordance with the precedent set in other Phase 3 psoriasis trials (Leonardi et al. 2008; Papp et al. 2008) and ixekizumab Phase 3 studies (RHAZ, RHBA, and RHBC).

6.2.1. Nonresponder Imputation (NRI)

Analysis of categorical efficacy and health outcomes variables will be assessed using a NRI method. Patients will be considered a nonresponder for the NRI analysis if they do not meet the clinical response criteria or have missing clinical response data at the analysis time point. Randomized patients without at least 1 post-baseline observation will also be defined as nonresponders for the NRI analysis.

6.2.2. Last Observation Carried Forward (LOCF)

A LOCF analysis will be performed on selected continuous efficacy and health outcomes variables as secondary analysis. For patients discontinuing investigational product for any reason, the last non-missing postbaseline observation before discontinuation will be carried forward to the corresponding endpoint for evaluation. Randomized patients without at least 1 post-baseline observation will not be included for evaluation.

6.3. Multiple Comparisons/Multiplicity

A gatekeeping testing strategy for the primary and major secondary analyses will be implemented to control the overall type I error rate at a 2-sided alpha level of 0.05. This will allow simultaneous inference of all of the primary and major secondary endpoints. The underlying procedure is derived using the methodology developed in Dmitrienko and Tamhane 2011. The gatekeeping procedure is based on the Bonferroni test and utilizes an intuitive, stepwise testing algorithm. The alpha levels for the p-values associated with the primary and secondary analyses are computed at each step depending on the outcomes of the preceding significance tests.

In order to reflect the test order and how the multiple doses will be analyzed, the doses have been renamed and the treatment comparisons to be performed in each dosing period are shown in [Table RHBH. 6.2.](#) (treatment groups will be presented as defined in Section 6.1.1).

Table RHBH. 6.2. Treatment Comparisons during the Induction Dosing Period and Maintenance Dosing Period

Induction Dosing	Treatment Group Comparisons during the Induction Dosing Period (Week 12)	Maintenance Dosing	Treatment Group Comparisons during the Maintenance Dosing Period (Week 60)
80 mg Q2W = Dose 1	Dose 1 versus Placebo	80 mg Q4W = Dose 1A Placebo = Dose 1B	Dose 1A versus Dose 1B
80 mg Q4W = Dose 2	Dose 2 versus Placebo	80 mg Q4W = Dose 2A Placebo = Dose 2B	Dose 2A versus Dose 2B

Abbreviations: Q2W = once every 2 weeks; Q4W = once every 4 weeks.

- Primary 1 (Test 1) – Proportion of patients with an sPGA (0, 1) at Week 12 (Visit 7) compared to placebo
- Primary 2 (Test 2) – Proportion of patients with PASI 75 at Week 12 (Visit 7) compared to placebo
- Secondary 1 (Test 3) – Proportion of patients achieving an sPGA (0) at Week 12 (Visit 7) compared to placebo
- Secondary 2 (Test 4) – Proportion of patients with PASI 90 at Week 12 (Visit 7) compared to placebo
- Secondary 3 (Test 5) – Proportion of patients with PASI 100 at Week 12 (Visit 7) compared to placebo
- Secondary 4 (Test 6) – Proportion of patients maintaining an sPGA (0,1) from Week 12 (Visit 7) after re-randomization at start of Maintenance Dosing Period to Week 60 (Visit 19) compared to placebo for ixekizumab-treated patients who had an sPGA (0,1) at Week 12 and were re-randomized
- Secondary 5 (Test 7) – Proportion of patients maintaining or achieving an sPGA (0) from Week 12 (Visit 7) after re-randomization at start of Maintenance Dosing Period to Week 60 (Visit 19) compared to placebo for ixekizumab-treated patients who had an sPGA (0,1) at Week 12 and were re-randomized
- Secondary 6 (Test 8) – Proportion of patients achieving an Itch NRS ≥ 4 point reduction from baseline at Week 12 (Visit 7) compared with placebo (for patients who had baseline Itch NRS ≥ 4)
- Secondary 7 (Test 9) – Change from baseline in DLQI at Week 12 (Visit 7) compared to placebo
- Secondary 8 (Test 10) – Change from baseline in NAPSI (for fingernails) at Week 12 (Visit 7) compared to placebo

The 10 statistical tests will be grouped into 2 parallel branches. The first branch includes tests of Dose 1 versus placebo in Period 2 (Induction Dosing Period) as well as Dose 1A versus Dose 1B in Period 3 (Maintenance Dosing Period). The second branch includes tests of Dose 2 versus placebo in Period 2 (Induction Dosing Period) as well as Dose 2A versus Dose 2B in Period 3 (Maintenance Dosing Period). Test 2 will be performed at a dose only if Test 1 of that dose is significant. Similarly, each test for a particular dose will be performed only if all prior tests of that dose are significant. For each dose, if a test is not significant, all subsequent tests are not significant.

Step 1: Test 1 for Doses 1 and 2 compared to placebo will be carried out using the Bonferroni procedure, that is, each test will be carried out at a 2-sided $\alpha = 0.025$.

Step 2: Test 2 for Doses 1 and 2 compared to placebo will be carried out using the Bonferroni procedure. If Test 1 for Dose 1 is significant, Test 2 for Dose 1 will be carried out at a 2-sided $\alpha = 0.025$ and, if Test 1 for Dose 2 is significant, Test 2 for Dose 2 will be carried out at a 2-sided $\alpha = 0.025$.

Steps 3 through 10 will be carried out similar to Step 2 with the current step depending on the result of the previous step.

There will be no adjustment for multiple comparisons for any other analyses.

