6.1.2. General Considerations for Analyses during Period 2 (Induction Dosing Period)

Period 2 starts after the first dose of study treatment (Visit 2, Week 0) and ends prior to the first injection of study treatment at Week 12 (Visit 7) or the early discontinuation visit (between Weeks 0 and 12). If a patient has Visit 7 but does not receive injection at Week 12 (Visit 7), the last recorded time for Visit 7 is used as the end time for Period 2.

Baseline for ITT and Safety Populations will be defined as the last available value before the first injection for efficacy, health outcomes, and safety analyses. In most cases, this will be the measure recorded at Week 0 (Visit 2). For efficacy/health outcome measures, if the patient does not take any injection, the last available value on or prior to randomization date will be used. Change from baseline (CFB) will be calculated as the visit value of interest minus the baseline value. For safety analyses using a baseline period, the baseline period is defined as the time from Visit 1 to the date/time of the first injection.

Comparisons between each ixekizumab treatment group (80 mg Q2W or 80 mg Q4W) and placebo will be performed for all analyses in Period 2.

The primary analysis method for treatment comparisons of categorical efficacy and health outcomes variables will be a logistic regression analysis with treatment as a factor using PROC Logistic. The odds ratio and the corresponding 95% CIs, as well as the treatment differences and the corresponding 95% CIs, will be reported. Secondary analysis will be conducted using a Fisher's exact test. In the case when logistic regression model does not produce statistical results due to sparse data, Fisher's exact test will be used.

For all categorical efficacy and health outcome variables that are collected at repeated visits, treatment group comparisons will be analyzed at each visit using the logistic regression model. Missing data will be imputed using the NRI method (Section 6.2.1).

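### The gatekeeping procedure is valid but leaves a completed dose branch's 0.025 unused; passing it to the other branch would keep overall error within 0.05 and could help the later tests that have no stated power

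*SAP*

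**What the plan says.** SAP 6.3 aims to "control the overall type I error rate at a 2-sided alpha level of 0.05" across the primary and major secondary endpoints with a Bonferroni-based gatekeeping procedure. It says the alpha levels "are computed at each step depending on the outcomes of the preceding significance tests".

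The algorithm then works as follows:

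- "The 10 statistical tests will be grouped into 2 parallel branches": one for 80 mg Q2W and one for 80 mg Q4W. Each runs through the same ten endpoints in the same order.
- Step 1 tests sPGA (0,1) at Week 12 for each dose at two-sided 0.025.
- Step 2 tests PASI 75 for a dose at 0.025 if that dose passed Step 1.
- "Steps 3 through 10 will be carried out similar to Step 2 with the current step depending on the result of the previous step".
- Within a branch, "each test for a particular dose will be performed only if all prior tests of that dose are significant". One failure ends the branch.

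Protocol 12.2.1.5 gives the same steps. Neither document says what happens to a branch's 0.025 after all ten of its tests are rejected.

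SAP 5.3 and protocol 12.1 give power above 99% at 0.025 for Tests 1, 2 and 6, and for maintenance of PASI 75, which is not in the gate. Tests 3, 4, 5, 7, 8, 9 and 10 have no stated power. Test 8 (itch) is limited to patients with baseline itch NRS of at least 4, and Test 10 (NAPSI) to patients with fingernail involvement.

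**The concern.** The introductory sentence leads one to expect alpha that moves with the results. The steps give two separate fixed sequences that stay at 0.025 from first test to last. Once one dose has won everything, its share of the error budget has no further use, yet the other dose is still held to 0.025.

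This matters for the later tests. A p-value between 0.025 and 0.05 in the remaining branch fails and also blocks every test after it. The situation is plausible here: protocol 9.4.1 reports higher Week 12 response rates with Q2W than with Q4W in the pivotal studies, so the Q2W branch could finish while the Q4W branch is less certain.

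**Working it through.** **1. Reproduce the plan's figures.** Alpha: 0.025 + 0.025 = 0.05. Arm sizes: 420 at 2:2:1 gives 168, 168 and 84. Re-randomised per dose: 168 × 0.70 = 117.6, split 2:1 into 78.4 and 39.2, which matches 78 and 39.

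Exact two-sided Fisher power at 0.025:

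- Week 12, 75% v 5%, 168 v 84: above 99.99%
- Week 60, 70% v 10%, 78 v 39: 99.9999%

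At 0.05 the Week 12 figure is still above 99.99% and the Week 60 figure is 99.99998%. The stated power is confirmed, and more alpha adds nothing usable there.

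**2. Does transfer keep overall error within 0.05?** The rule examined: if one branch rejects all ten tests, the other resumes in the same order at 0.05 from its first non-rejected test.

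- *Both branches contain a true null.* A branch can pass on its alpha only after rejecting its own true null at 0.025. Any error made after a transfer therefore follows an error already made at 0.025. The chance of an error is at most 0.025 + 0.025 = 0.05.
- *Only one branch contains a true null.* An error requires rejecting the first true null in that branch, which is tested at no more than 0.05.

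Neither step needs independence between tests. Anything rejected at 0.025 is also rejected at 0.05, so the rule can only add rejections.

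A simulation of 400,000 runs agrees. It assumed endpoint correlation 0.5, and between-dose correlation 2/3 at Week 12 (shared placebo arm) and 0 for Tests 6 and 7. The documents give none of these values.

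| Truth | Overall error, fixed split | With transfer |
|---|---|---|
| All nulls true | 0.044 | 0.044 |
| One dose fully effective, other null | 0.025 | 0.050 |
| One dose fully effective, other null on Test 10 only | 0.0253 | 0.0503 |

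The Monte Carlo standard error near 0.05 is √(0.05 × 0.95 / 400,000) = 0.0003, so 0.0503 is consistent with 0.05.

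**3. Gain for one test once the other branch has completed.** The normal critical values are 2.2414 (two-sided 0.025) and 1.9600 (two-sided 0.05), a difference of 0.2814. If power at 0.025 is *p*, power at 0.05 is Φ(Φ⁻¹(*p*) + 0.2814). The starting powers are assumptions, because the documents give no effect size, SD or subset size for these tests.

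| Assumed power at 0.025 | Φ⁻¹(*p*) + 0.2814 | Power at 0.05 |
|---|---|---|
| 50% | 0.2814 | 61% |
| 70% | 0.8058 | 79% |
| 80% | 1.1230 | 87% |
| 90% | 1.5630 | 94% |
| 99% | 2.6077 | 99.5% |

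The largest gain is 11.2 points, at about 44% power.

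**4. Gain when both branches are uncertain.** In the same simulation, with Test 10 equally uncertain in both branches and all other tests near 100% power, per-dose power for Test 10 rises from 0.80 to 0.84, or from 0.50 to 0.55.

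**The case against.** The strongest reply is that this is a legitimate design choice. Bonferroni across doses with a fixed sequence within each dose is valid, is prespecified identically in both documents, and uses the same 0.025 as the sample-size calculation. Two statisticians given Steps 1 to 10 would run the same procedure. Transfer acts only if one dose wins all ten tests, including two at Week 60, and the other dose then has a p-value between 0.025 and 0.05. The fixed split also has a lower actual error, 0.025 against 0.05, when one dose works and the other does not. All of that stands. It limits the size of the point, but it does not show that the unused 0.025 is needed to meet the plan's own 0.05 target.

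Three stronger readings are tempting, and the documents do not support them.

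- *SAP 6.3 contradicts itself.* The sentence on alpha levels is loose rather than false. Each level does depend on the previous result, in that a test is either run at 0.025 or not run.
- *The plan loses power on its main comparisons.* The co-primary tests and the Week 60 sPGA (0,1) test exceed 99.99% power at 0.025 under the planned rates.
- *The 95% intervals are at odds with gated tests at 0.025.* SAP 6.1.2 says the odds ratios, "as well as the treatment differences and the corresponding 95% CIs, will be reported", but nothing uses those intervals to decide the gate. Moving to 97.5% would not guarantee agreement either. A test blocked by an earlier failure can still have an interval that excludes no effect, and an interval for a difference in proportions need not match a logistic regression p-value.

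**Conclusion.** The point holds as an efficiency improvement, not as a type I error flaw. The procedure controls overall error at 0.05, but it is stricter than that limit requires once a branch has completed.

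The possible gain is roughly 0 to 11 percentage points for a single test with no stated power, conditional on the other dose having won all ten. It is about 4 to 5 points per dose if Test 10 is equally uncertain in both branches at 80% or 50% power. The conditional range rests on assumed starting powers and a normal approximation, and the second figure also rests on the simulation's assumed correlations. The error-control argument rests on neither. Tests with stated power are unaffected. A failed test would still block later ones under the new rule; only the threshold changes.

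**What to change.** Before any unblinding, add the same rule to SAP 6.3 and protocol 12.2.1.5: if all ten tests in one dose branch are rejected at 0.025, that 0.025 passes to the other branch, which resumes in the same order at two-sided 0.05 from its first non-rejected test.

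The programming is minor. The wording must change in both documents, because an SAP-only change would leave them in conflict on multiplicity. Protocol 12.2.1 requires an amendment when a principal feature changes, and the alpha rule is arguably one. The statistical cost is the rise in actual error from 0.025 to 0.05 when one dose is fully effective and the other null, which stays at the stated limit.

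Timing decides whether this can be done. SAP 6.15 allows unblinding at a Week 60 lock, and the SAP revision history places Version 2 only before the final lock. If unblinding has already occurred, leave the procedure as it is and only reword the sentence on alpha levels, in both documents, to say that each branch is tested at a fixed two-sided 0.025.

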6.4. Patient Disposition

Patient flow will be summarized from entered, to randomized, and to completion, and analysis populations will be listed and summarized by treatment group.

Patient disposition from study will be listed for the ITT population and summarized with reasons for disposition for the ITT population and the follow-up population, respectively. Patient disposition from study due to COVID-19 will also be listed.

Patient disposition from study treatment will be listed for the ITT population and summarized for the ITT population in Period 2 and the Maintenance Dosing Period Primary/Secondary/Relapse Population in Period 3 with reasons for disposition. Fisher's exact test will be used to test for a difference between and among treatment groups for the ITT population in Period 2 and the Maintenance Dosing Period Primary Population in Period 3. Patient disposition from study treatment due to COVID-19 will also be listed. The time to study treatment discontinuation due to any reason (in weeks) will be summarized by treatment group and graphically using Kaplan-Meier techniques, for each treatment period. The log-rank test will be used to compare time to study treatment discontinuation between treatment groups. The time to study treatment discontinuation will be calculated as:

$$\frac{\text{Date of study treatment discontinuation in period} - \text{Date of first dose in period} + 1}{7}$$

For Induction Dosing period, if the date of first dose is missing, the date of randomization will be used. Patients completing the study treatment will be censored at the date of completion (that is, the date of the last scheduled visit in the period). For the analyses of Period 3, if a patient

experiences relapse during the period, they will be censored at the date of relapse (Analysis populations: ITT Population, Maintenance Dosing Period Primary Population)

Patient allocation by center/site will be summarized with number of patients who entered the study, number of ITT patients for each treatment group, number of patients discontinued from study treatment, and number of patients discontinued from study.

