- Patients receiving 80 mg ixekizumab Q4W, who relapse, will continue on 80 mg ixekizumab Q4W in order to maintain the study blind and to evaluate the long term efficacy of ixekizumab treatment.
- Patients receiving placebo who relapse will be switched to 80 mg ixekizumab Q4W.

Continued treatment for patients who relapse is provided to understand the longer-term efficacy of ixekizumab when treating patients who experience relapse and to maintain study blinding. See Section 8.3.1 for discontinuation criteria.

**Treatment Assignment for Non-Responders:** Patients randomized to ixekizumab at Week 0 (Period 2) who are non-responders at Week 12 (Visit 7) will receive treatment with 80 mg ixekizumab Q4W during Period 3.

Patients randomized to placebo at Week 0 (Period 2) who are non-responders at Week 12 (Visit 7) will receive treatment with 80 mg ixekizumab Q4W during Period 3. These patients will receive a starting dose of 160 mg ixekizumab as 2 SC injections at Week 12 (Visit 7).

Continued treatment for non-responders is provided so that partial or slow responders to ixekizumab and non-responders to placebo may remain in the study and receive treatment with ixekizumab while maintaining the study blind. Some patients may be deriving benefit from treatment with ixekizumab but will be slow responders or partial responders thereby not meeting the “responder” criteria at Week 12. A discontinuation criterion for patients who remain at or above their baseline sPGA score at both Week 12 and Week 24 is included (see Section 8.3.1) to ensure that patients who have not shown any benefit from treatment with ixekizumab can be treated with any other psoriasis therapy as determined appropriate by the investigator.

Once a patient has switched to 80 mg Q4W, regardless of original treatment in Period 2, re-randomization in Period 3, or any assessments of response/relapse, the patient will remain on 80 mg Q4W.

Patients who discontinue the study for any reason during Period 3 will stop treatment and continue to the ETV prior to entering the Post-Treatment Follow-Up Period (Period 4; Section 7.1.4).

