### **8.3. Discontinuation Criteria**

The reason for and date of discontinuation from study treatment (investigational product) and reason for and date of discontinuation from study participation will be collected for all randomized patients. For patients who discontinue because of death and lost to follow up, only the reason for and date of discontinuation from study participation will be collected.

For any patient discontinued from the study treatment, the investigational product will be withheld, and the patient will complete the ETV and the Post-Treatment Follow-up Period (Period 4), as shown in the Study Schedule ([Attachment 1](#)).

Missing data may compromise the integrity of the study. Complete information from each patient is critical to achieving the fullest understanding of the potential benefits and risks of

ixekizumab. All efforts should be made to keep patients in the study, to attend scheduled visits and procedures, and to take investigational product as medically appropriate.

Patients who meet any of the criteria described in Section 8.3.1.1 will be discontinued from study treatment.

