5.3. Determination of Sample Size

The total sample size for the study is 420 patients randomized at a 2:2:1 ratio in the blinded Induction Dosing Period to 80 mg Q2W, 80 mg Q4W, and placebo, respectively. In order to account for multiple testing for the 2 ixekizumab groups, a 2-sided Fisher's exact test at the 0.025 level is assumed. Assuming the response rates for both sPGA (0,1) and PASI 75 at Week 12 (Visit 7) are 75% for each ixekizumab treatment group and 5% for the placebo group, 168 patients in 80 mg Q2W or 80 mg Q4W versus 84 patients in placebo group will provide >99% power to test the superiority of each ixekizumab dose regimen to placebo for sPGA (0,1) and for PASI 75. These assumptions are based on the integrated results from the pivotal Phase 3 Studies RHAZ, RHBA, and RHBC.

Assuming 70% of the ixekizumab patients are re-randomized in the Maintenance Dosing Period at Week 12 (Visit 7) at a 2:1 ratio to 80 mg Q4W or placebo, approximately 78 patients will be included in 80 mg Q4W group and 39 patients in placebo group. This sample size will:

- provide >99% power to test the difference in the proportion of patients maintaining sPGA (0, 1) from Week 12 (Visit 7) after re-randomization at start of Maintenance Dosing Period to Week 60 (Visit 19) in the Maintenance Dosing Period Primary population between the ixekizumab dosing interval and placebo within the original treatment group, assuming the proportions of patients maintaining sPGA (0, 1) are 70% for 80 mg Q4W and 10% for placebo within each original treatment group (Visit 19). A 2-sided Fisher's exact test at the 0.025 significance level is assumed.
- provide >99% power to test the difference in the proportion of patients maintaining a PASI 75 from Week 12 (Visit 7) after re-randomization at start of Maintenance Dosing Period to Week 60 (Visit 19) in the Maintenance Dosing Period Primary population

between the ixekizumab dosing interval and placebo within each original treatment group, assuming the proportions of patients maintaining a PASI 75 are 70% for 80 mg Q4W and 10% for placebo within each original treatment group. A 2-sided Fisher's exact test at the 0.025 significance level is assumed.

6. A Priori Statistical Methods

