6.1.1. Analysis Population

The following major analysis populations will be used (additional analysis populations for specific analysis will be defined in the corresponding analysis section):

Intent-to-Treat Population (ITT): Unless otherwise specified, efficacy and health outcomes analyses for Period 2 (Induction Dosing Period) will be conducted on the intent-to-treat (ITT) population, defined as all randomized patients, even if the patient does not take the assigned treatment, does not receive the correct treatment, or otherwise does not follow the protocol. Patients will be analyzed according to the treatment to which they are assigned.

Per Protocol Set (PPS): In addition, the primary analysis will be repeated using the per protocol set (PPS), which is defined as all randomized patients who are compliant with therapy, who do not have a subset of important protocol deviations that impact the primary efficacy endpoint (Section 6.5), and whose investigator site does not have significant good clinical practice (GCP) issues that require a report to the regulatory agencies prior to Week 12 (Visit 7). Compliance with therapy is defined to be missing no more than 20% of expected doses, not missing 2 consecutive doses, and no double dosing (that is, taking more injections at the same time point than specified in the protocol) during the period that patients participated in the study and prior to Week 12 (Visit 7) (see Section 6.8). Patients will be analyzed according to the treatment to which they are assigned.

Safety Population: Safety analyses for Period 2 will be conducted on the Safety Population, defined as all randomized patients who received at least 1 dose of study treatment. Patients will be analyzed according to the treatment to which they were assigned.

Maintenance Dosing Period Primary population: defined as all re-randomized patients (that is, patients randomized to ixekizumab in Period 2 who achieved an sPGA (0, 1) and were re-randomized at Week 12) who received at least 1 dose of study treatment during Period 3.

Patients will be analyzed according to the treatment to which they were re-randomized. Only information prior to relapse will be presented.

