Maintenance Dosing Period Secondary population: defined as the ixekizumab patients who were not re-randomized at Week 12 or patients who were randomized to placebo at Week 0, who received at least 1 dose of study treatment during Period 3. Patients will be analyzed according to the treatment to which they were assigned upon entry into Period 3.

Maintenance Dosing Period Relapse population: defined as all patients who were responders at Week 12 (that is, patients who achieved an sPGA (0,1) at Week 12) who first experience a relapse (sPGA ≥ 3) at any point during the maintenance dosing period (that is, Period 3). Although all patients will receive 80 mg Q4W, patients will be analyzed according to the treatment to which they were re-randomized or assigned at Week 12 (see treatment groups defined in [Table RHBH. 6.1.](#)).

Follow-up Population: Safety analyses for Period 4 (Post-Treatment Follow-up Period) will be conducted on the follow-up population, defined as all randomized patients who received at least 1 dose of study treatment and have entered the post-treatment follow-up period. Patients will be analyzed according to the treatment they actually received prior to entering Period 4.

[Table RHBH. 6.1.](#) describes the treatment groups and the comparisons for each study period and the analysis population.

Table RHBH. 6.1. Treatment Groups and Comparisons for Each Study Period and Analysis Population

Study Period	Analysis Population	Treatment Group	Abbreviation	Comparison
Induction Dosing Period (Period 2)	Intent-to-Treat Population; Per Protocol Set; Safety Population	Placebo	PBO	IXE80Q4W vs. PBO; IXE80Q2W vs. PBO; Overall ^a
		Ixekizumab 80 mg Q4W	IXE80Q4W	
		Ixekizumab 80 mg Q2W	IXE80Q2W	
		Total Ixekizumab	Total IXE	
		Total	Total	
Maintenance Dosing Period (Period 3)	Maintenance Dosing Period Primary Population (by Individual Dose)	Ixekizumab 80 mg Q4W/Placebo	IXE80Q4W/PBO	IXE80Q4W/IXE80Q4W vs IXE80Q4W/PBO; IXE80Q2W/IXE80Q4W vs IXE80Q2W/PBO Overall ^a
		Ixekizumab 80 mg Q4W/Ixekizumab 80 mg Q4W	IXE80Q4W/IXE80Q4W	
		Ixekizumab 80 mg Q2W/Placebo	IXE80Q2W/PBO	
		Ixekizumab 80 mg Q2W/ Ixekizumab 80 mg Q4W	IXE80Q2W/IXE80Q4W	
		Total	Total	
	Maintenance Dosing Period Primary Population (by Pooled Dose)	Ixekizumab/Placebo	IXE/PBO	IXE/IXE vs IXE/PBO
		Ixekizumab/Ixekizumab	IXE/IXE	
		Total	Total	
	Maintenance Dosing Period Secondary Population ^b	PlaceboResp/Placebo	PBOResp/PBO	No Comparison
		PlaceboNonR/Ixekizumab 80 mg Q4W	PBONonR/IXE80Q4W	

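### The Period 3 Kaplan-Meier curve for stopping study treatment censors at relapse, so it does not show the share who stop before relapse and leaves out stops that come later

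*SAP*

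**What the plan says.** SAP 6.4 measures the time from first dose in the period to discontinuation of study treatment, whatever the cause, and displays it by Kaplan-Meier. It adds that "The log-rank test will be used to compare time to study treatment discontinuation between treatment groups". Completers are censored at completion. For Period 3, if a patient "experiences relapse during the period, they will be censored at the date of relapse". The Period 3 analysis is run in the Maintenance Dosing Period Primary Population.

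Treatment continues past relapse in every re-randomised arm. Under Protocol 7.1.3, ixekizumab patients "who relapse, will continue on 80 mg ixekizumab Q4W in order to maintain the study blind", and placebo patients are switched to ixekizumab 80 mg Q4W.

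Three other provisions bear on the point:
- SAP 6.1.1 says of the Primary Population: "Only information prior to relapse will be presented".
- SAP 6.4 also has treatment disposition "summarized for the ITT population in Period 2 and the Maintenance Dosing Period Primary/Secondary/Relapse Population in Period 3 with reasons for disposition". SAP 6.1.1 defines the Relapse Population as Week 12 responders "who first experience a relapse (sPGA ≥ 3) at any point during the maintenance dosing period" and shows it by the group assigned at Week 12.
- For patients who die or are lost to follow-up, Protocol 8.3 says "only the reason for and date of discontinuation from study participation will be collected".

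**The concern.** Kaplan-Meier reads as a proportion only if a censored patient could still have had the event later at the same rate as those left under observation. Relapse does not fit that in either arm, for different reasons.

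In the withdrawal arms (ixekizumab, then placebo), relapse ends the assigned placebo. After that the patient cannot stop placebo before relapse. Relapse is a competing event, and treating it as ordinary censoring makes one minus Kaplan-Meier larger than the proportion who stop before relapse. The disposition table in the same section, read with the pre-relapse rule in 6.1.1, would give the smaller crude proportion for the same patients, with nothing to explain the difference.

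In the ixekizumab/ixekizumab arms, relapse changes nothing about treatment. Censoring there removes genuine later stops of the assigned drug from an endpoint that claims to cover any cause.

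At stake is a tolerability and persistence figure that a reader would naturally take as the share of each arm that stopped treatment.

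**Working it through.** **The plan's own figure.** The documents give no expected discontinuation or relapse rate for Period 3. What can be reproduced is the Week 60 power in SAP 5.3, "assuming the proportions of patients maintaining sPGA (0, 1) are 70% for 80 mg Q4W and 10% for placebo". Arm sizes: 0.70 × 168 = 117.6 per induction regimen, split 2:1 into 78.4 and 39.2, matching 78 and 39. Exact Fisher power at two-sided 0.025 is 0.999999, so the stated value above 99% holds.

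**Inputs.**
- Stopping rate: the protocol synopsis plans 336 completers of 420, or 80%. Assuming a constant hazard over 60 weeks, d = −ln(0.80)/60 = 0.00372 per week.
- Period 3 length: T = 48 weeks.
- Relapse in the withdrawal arms: assumed 50% to 90%. The plan's 10% maintaining response on placebo makes 90% an upper bound, because the remainder also contains patients at sPGA 2 and patients counted as non-responders for missing data.

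**What the planned curve estimates.** With relapse censored, 1 − KM = 1 − exp(−d × T) = 1 − exp(−0.1785) = 16.3%, or 6.4 of 39, whatever the relapse rate.

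**Share who stop before relapse.** With relapse hazard r, the crude relapse proportion is R = r/(d + r) × [1 − exp(−(d + r)T)]. The cumulative incidence of stopping before relapse has the same form with d in the numerator, so it equals R × d/r.

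| R | r per week | Stop before relapse | Of 39 | 1 − KM divided by this |
|---|---|---|---|---|
| 50% | 0.0162 | 11.5% | 4.5 | 1.4 |
| 70% | 0.0288 | 9.0% | 3.5 | 1.8 |
| 80% | 0.0396 | 7.5% | 2.9 | 2.2 |
| 90% | 0.0609 | 5.5% | 2.1 | 3.0 |

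Halving d gives 8.5% from the curve against 6.1% to 3.1%. Multiplying d by 1.5 gives 23.5% against 16.3% to 7.2%. The direction does not change.

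**All Period 3 stops, including after relapse.** Let the hazard after relapse be h × d. Stops after relapse are the integral over s from 0 to T of r·exp(−(d + r)s) × [1 − exp(−h·d·(T − s))]. In a withdrawal arm with 80% relapse, the total is:

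| h | 0.25 | 0.5 | 1 | 2 | 3 |
|---|---|---|---|---|---|
| All stops | 9.8% | 12.1% | 16.3% | 24.1% | 30.8% |

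The curve's 16.3% is too high if stopping slows after relapse, right if it is unchanged, and too low if it speeds up. No document gives h.

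**Ixekizumab/ixekizumab arms.** Take 30% relapse, the upper bound implied by 70% maintaining response. Then r = 0.00821, and stops before relapse are 0.30 × 0.00372/0.00821 = 13.6%. With h = 1, total stops are 16.35%, so the part after relapse is 16.35 − 13.59 = 2.76%, about 2.2 of 78 patients. Those stops are absent from the curve and the log-rank test. With h = 2 the total is 18.8%, against 16.3% from the curve.

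**The case against.** The strongest defence is that the censoring follows a stated rule. SAP 6.1.1 limits the Primary Population to information before relapse, and the exposure calculation in 6.12.1.2 uses the same cut-off. On that footing the log-rank test compares pre-relapse cause-specific hazards, which is legitimate. This stands for the test. It does not rescue the curve, because a cause-specific hazard does not convert to a proportion through Kaplan-Meier when a competing event is common.

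A reader might infer that stops after relapse are lost to the study. They are not: SAP 6.4 tabulates them with reasons for the Relapse Population and lists treatment disposition for all ITT patients, and 6.12 and 6.12.2 add discontinuations due to adverse events. They are missing only from this time-to-event analysis.

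A reader might also infer that the curve overstates all stopping in the withdrawal arms, or that the comparison is tilted towards ixekizumab. That would require counting only pre-relapse stops in one arm and all stops in the other. Counted alike, the sign depends on the post-relapse stopping rate, which the documents do not give. For the same reason a different definition by arm would be a poor remedy: with equal stopping hazards it would create a gap of its own.

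Finally, the sizes rest on assumed rates, and the analysis is neither an objective nor a gated test. Both are correct and limit the priority.

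**Conclusion.** The point holds in a limited form. As planned, the Period 3 curve in the withdrawal arms would not estimate the proportion who stop before relapse. Under constant hazards, planned completion of 80% and 50% to 90% relapse, it reads about 16% where the true share is 11.5% to 5.5%, a ratio of about 1.4 to 3.0, and it would not agree with the pre-relapse disposition table. In the ixekizumab/ixekizumab arms it leaves out later stops of an unchanged treatment, about 2 of 78 patients in the illustration. The mechanism follows from the text alone; the sizes do not. Whether all Period 3 stopping is over- or understated, and whether either arm benefits, cannot be determined.

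The dating of deaths and losses to follow-up is a gap in detail only: SAP 6.4 needs a treatment-discontinuation date that Protocol 8.3 does not collect for them, but their study-discontinuation date is collected.

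Priority is minor. No efficacy conclusion or gated comparison depends on this display.

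**What to change.** Amend SAP 6.4 for Period 3, using the same definition in every arm:

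1. Replace the Kaplan-Meier curve with the cumulative incidence of treatment discontinuation before relapse, with relapse as a competing event. Keep the log-rank test, labelled as the pre-relapse cause-specific comparison.
2. Add an any-cause time-to-discontinuation analysis to Week 60 by assigned group, without censoring at relapse, in which the event is stopping study treatment, including ixekizumab given after a switch.
3. State that deaths and losses to follow-up are dated by the study-discontinuation date.

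The cost is SAP wording and programming, with no new data. There will be one additional curve to explain, and item 2 needs an explicit exception to the rule in SAP 6.1.1 that confines the Primary Population to pre-relapse information.
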